The ceftriaxone to PRevent pneumOnia and inflammaTion aftEr Cardiac arrest (PROTECT) randomizedcontrolled trial and resistome assessment will evaluate the impact of prophylactic ceftriaxone on earlyonset pneumonia (EOP) in patients resuscitated from out-of-hospital cardiac arrest (OHCA) and are comatose. The trial will build upon the findings from observational studies and the Antibiotherapy during Therapeutic Hypothermia to Prevent Infectious Complications (ANTHARTIC) trial.¹⁻³

The PROTECT trial is a multi-center, randomized-controlled, quadruple-blind, non-commercial superiority trial in which prophylactic ceftriaxone for three days after OHCA will be compared with standard care. The trial will also study ceftriaxone's ability to suppress T-cell-mediated inflammation via increased CD73/ adenosine signaling. It will also determine the effect of prophylactic ceftriaxone on the bacterial resistome using metagenomic sequencing and resistance genotype expression.

Patients ≥18 years of age will be eligible for enrollment if they are admitted to the hospital following OHCA and are comatose. The traditional informed consent process will take place prior to any study procedures. Exception from Informed Consent (EFIC) will be invoked when a family member or legal authorized representative (LAR) is unavailable at xxxx. Bedside clinicians, study investigators, patients and outcome adjudicators will be blinded to group allocation.

All patients will receive guideline-recommended treatment. Targeted temperature management (TTM) at a patient-specific goal may be used. Neurological monitoring may include the bispectral index (BIS) and continuous electroencephalography (cEEG) until it is deemed clinically unnecessary. Seizures will be aggressively treated according to clinical practice guidelines. Sedation and analgesia will be minimized to prevent interference with neurological prognostication while still providing comfort.

Patients will be randomized 1:1 to ceftriaxone 2 gm intravenously (IV) every 12 hours for three days or matching placebo. All other aspects of care will be the same between groups. Patients will undergo shotgun metagenomics sequencing to evaluate their bacterial resistome using nucleic acids obtained from sputum samples and rectal swabs. The impact of ceftriaxone on inflammation will be examined through T-cell-mediated inflammation via CD73/ adenosine signaling.

All patients will have their neurological prognosis assessed per the European Resuscitation Council (ERC's) recommendations after OHCA. Follow-up assessment will be performed six months after cardiac arrest using the modified Rankin Scale (mRS) and Cerebral Performance Category (CPC). A good functional outcome will be defined as a mRS ≤0-3 of or a CPC 1-2. Data from this trial will be used to conduct a power calculation for multicenter study examining mortality and functional outcome.

2. Scientific Justification and Significance

OHCA occurs in ~350,000 adults each year in the United States.⁴ Initial heart rhythm, as determined by emergency medical services (EMS) automated external defibrillators, is ventricular fibrillation (VF) or ventricular tachycardia (VT) in 19% of patients. Among EMS-treated patients suffering OHCA, the incidence of survival and good functional status at hospital discharge was 10.5% and 8.5% in 2019, respectively.⁴ Survival to hospital discharge has remained unchanged over the past five years, suggesting an urgent need for therapeutic advancements.

2.1. Post-resuscitation Care

Resuscitation from OHCA continues after return of spontaneous circulation (ROSC) is achieved. Clinical practice guidelines published by the American Heart Association in 2020 provide an evidenced-based approach to post-resuscitation care.⁵ During the initial stabilization phase, the airway is secured, respiratory parameters are optimized, and hemodynamic derangements are corrected. These processes may occur independently or concurrently during the initial stabilization phase.

Additional emergent activities are conducted concurrently once initial stabilization has been achieved. Continued management includes treating reversible etiologies of OHCA such as ST-segment elevation myocardial infarction or pulmonary embolism. Emergent activities minimize secondary hypoxic-ischemic injury to the brain and may include TTM, maintenance of normoxia and euglycemia, provision of continuous or intermittent encephalography, and lung-protective mechanical ventilation.⁵

TTM between 32-36°C (COR 1, LOE B-R) for 24 hours (COR 2a, LOE B-NR) is recommended for adults who remain comatose after OHCA (COR 1, LOE B-R).⁵ Recommendations are based on two trials examining TTM (32°C to 34°C) in patients with OHCA with an initially shockable heart rhythm, one trial examining TTM (33°C to 37°C) in patients with in-hospital or OHCA with an initially non-shockable heart rhythm, one trial examining TTM (33°C to 36°C) in patients with OHCA any initial heart rhythm, and one trial examining TTM (33°C) for 24 vs. 48 hours.

Clinical practice guidelines suggest a mean arterial pressure (MAP) >65 mmHg (COR 2a, LOE B-NR), at a minimum.⁵ Normoxia with an oxygen saturation of 92% to 98% should be maintained while avoiding hyperoxia (COR 2b, LOE B-R).⁵ Ventilation should be adjusted to maintain an arterial partial pressure of carbon dioxide within 35-45 mmHg (COR 2b, B-R).⁵ Seizures should be monitored for with intermittent or cEEG and treated aggressively (COR 1, LOE C-LD).⁵

2.2. Pneumonia after Cardiac Arrest

Pneumonia is an infection of the lungs resulting in alveolar inflammation and fluid or purulent material accumulation. It is the most common infection after cardiac arrest occurring in up to 65% of patients treated with TTM.⁶ Infections are associated with increased intensive care unit (ICU) length of stay (LOS), hospital LOS, duration of mechanical ventilation, post-discharge rehabilitation need, tracheostomy, and mortality, while also reducing the incidence of a good functional outcome.⁷⁻¹¹

Pneumonia results from aspiration during cardiopulmonary resuscitation (CPR), or by introduction of oropharyngeal flora into the lungs during airway management. It may also be due to gastrointestinal hypoperfusion, which leads to ischemic injury to the intestinal mucosa, bacterial translocation, and hematogenous spread. Infection might also be the result of post-resuscitation immune suppression.¹²⁻¹⁸ The association between infection and morbidity and mortality justifies further study.

Preventing infection after OHCA may: 1) reduce exposure to broad-spectrum antibiotics and subsequent collateral damage, 2) prevent hemodynamic derangements due to local and systemic inflammation, and 3) prevent an association between infection and morbidity and mortality. These benefits must be balanced with the risk for altering bacterial resistomes in the absence of clinical infection. Accordingly, further study is warranted to understand the risk-to-benefit ratio of prophylactic antibiotics.

2.3. Antibiotic Prophylaxis in Comatose Patients after Acute Brain Injury

The first trial was a single-center, prospective, randomized-controlled, open-label study of cefuroxime 1.5 grams IV q12h for two doses in a heterogeneous cohort of patients requiring mechanical ventilation after head injury or stroke resulting in a Glasgow Coma Scale (GCS) ≤ 12 .¹⁹ Study drug was started <6 hours from the time of intubation. EOP occurred ≤ 4 days from the initiation of mechanical ventilation. A total of 100 subjects were included with 50 in each group. Incidence of EOP was 16% in the cefuroxime group and 36% in controls (p=0.02).

The second trial was a single-center, prospective, randomized-controlled, open-label study of ampicillinsulbactam 3 gm IV q6h for 72 hours in a heterogeneous cohort of patients requiring mechanical ventilation after head injury or stroke resulting in a GCS $\leq 8.^{20}$ Study drug was started <6 hours from the time of ICU admission. EOP occurred ≤ 4 days from the initiation of mechanical ventilation. A total of 36 subjects were included with 18 in each group. Incidence of EOP was 21% in the ampicillin-sulbactam group and 58% in controls (p=0.02).

The third study was a single-center, prospective, before-and-after study of single-dose ceftriaxone in a heterogeneous cohort of patients requiring mechanical ventilation after head injury or stroke resulting in a GCS $\leq 8.^{21}$ Study drug was started <4 hours from the time of initiation of mechanical ventilation. Early-onset pneumonia occurred ≤ 4 days from the initiation of mechanical ventilation. A total of 129 subjects were included with 71 in the ceftriaxone group and 58 in the controls. Incidence of EOP was 2% in the ceftriaxone group and 22% in controls (p=0.001).

Although other publications have reported on the impact of antibiotic prophylaxis following acute brain injury, their methodology was less rigorous. In a single-center, retrospective, before-and-after study of ceftriaxone 2 gm IV for one dose in 172 intubated patients the incidence of EOP was reduced significantly (7.4 vs 19.8%, p=0.026).²² A post-hoc analysis of the SPIRIT-ICU and CORTI-TC studies of traumatic brain injury determined antibiotic prophylaxis reduced EOP compared to no prophylaxis (10% vs. 32%; p<0.01).²³

2.4. Antibiotic Prophylaxis after Cardiac Arrest

A meta-analysis, published in 2019, reported three randomized-controlled trials and eight observational studies have compared prophylactic or early antibiotics to clinically-driven or delayed antibiotics.²⁴ Results were hampered by the fact that two of the three randomized-controlled trials were published in abstract form only. In the overall analysis, which inappropriately combined randomized and observational studies, prophylactic or early antibiotics were not associated with a reduced incidence of combined early- and late-onset pneumonia (OR 0.58, 95% CI 0.23–1.46).

The ANTHARTIC trial, published in 2019, randomized 198 patients who suffered OHCA due to a shockable rhythm to amoxicillin-clavulanate 1 gram/ 200 mg IV every 8 hours or placebo administered for 48 hours starting within six hours of ROSC.³ The incidence of EOP within the first seven days was reduced (19% vs. 34%; HR 0.53; 95% CI 0.31 to 0.92; p=0.03), and remained similar when the definition for EOP was changed to \leq 5 days (17% vs. 31%, HR 0.53; 95% CI, 0.30 to 0.95; p=0.03).

The PROTECT trial will expand the findings of the ANTHARTIC trial in several ways: 1) inclusion of OHCA patients with all initial heart rhythms, 2) use of a lower-risk antibiotic available in the USA that has not previously been tested after OHCA, 3) study the anti-inflammatory effects of ceftriaxone to determine a

mechanism by which it may improve clinical outcomes, and 4) complete a metagenomics assessment of bacterial resistomes pre- and post-ceftriaxone prophylaxis.

2.5. Antibiotic Resistance and the Resistome

The effect of antibiotic prophylaxis on bacterial resistance after OHCA are not known, but antibiotic resistance is a global concern.²⁵ Emergence of resistant bacteria will be examined in treatment and control patients. Control patients may be exposed to longer courses of broad spectrum antibiotics due to higher rates of pneumonia. Drug concentrations in stool, effects of ceftriaxone on expression of resistance genes, and on richness, diversity, and relative abundance of taxa will be quantified.

Prior studies have concluded antibiotic prophylaxis in acutely brain-injured patients does not induce bacterial resistance based on limited analyses. For example, in the trial examining cefuroxime prophylaxis, the intervention did not induce bacterial resistance based similar rates in gram-negative bacilli pneumonia in both groups.¹⁹ Advances in metagenomics allows for sample multiplexing and depth of sequence coverage (20 million reads) for the measurement of resistomes of each individual patient.

The ANTHARTIC trial evaluated intestinal acquisition of multidrug-resistant bacteria on day seven on solid selective media using stool samples, limiting their observations to conditionally cultivatable organisms.³ No difference was found following two days of amoxicillin-clavulanate administration compared to placebo. The contemporary gold standard for evaluating bacterial resistance is resistome analysis with high-throughput sequencing, which will be utilized in the PROTECT trial.

2.6. Anti-inflammatory Effects of Ceftriaxone

Ceftriaxone reduced IFN- γ and TNF- α in the injured parietal cortex and improved learning and spatial memory function in a rat model of traumatic brain injury.²⁶ Ceftriaxone also reduced IFN- γ and IL-17 secretion in a mouse model of multiple sclerosis by altering antigen presentation and activation of myelin-specific T lymphocytes.²⁷ Other studies have shown ceftriaxone dampens excitotoxicity in by decreasing glutamate transporter function.^{26,28-31} Because excitotoxicity is a possible cause of secondary brain injury following OHCA, ceftriaxone's ability to attenuate this response is promising.³²

T cells promote neuroinflammation and neuronal cell death via IFN- γ and TNF- α .³²⁻³⁴ Our preliminary data showed incubation of CD3+ T-cells from human peripheral blood with ceftriaxone for 24 hours increased expression of CD73. CD73 is an adenosine-generating enzyme, and adenosine has potent immunosuppressive and anti-inflammatory effects in T cells. Consistent with this concept, the PROTECT study will determine if CD73 level is inversely correlated with IFN- γ levels in both CD4+ and CD8+ T cells.

2.7. Study Hypothesis and Anticipated Results

Prophylactic ceftriaxone administered within six hours of ICU admission will reduce the incidence of EOP and T cell-mediated inflammation in comatose OHCA survivors. Additionally, prophylactic ceftriaxone will not negatively affect bacterial resistomes as assessed by resistance genotypes in stool or sputum.

3. Trial Design

The PROTECT trial was a single-center, randomized-controlled, quadruple-blind, non-commercial superiority trial conducted at xxxx. The inflammation analysis will be completed at xxxx. The resistome analysis will be done at xxxx and xxxx.

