9.1. Sample Size

Incidence of EOP without antibiotic prophylaxis is unclear due to low-quality studies, variable definitions for EOP, varying diagnostic criteria, and inconsistent reporting of antibiotic administration. Additionally, studies examine early antibiotics, which may be symptom-driven *or* prophylactic.

In the ANTHARTIC trial, the incidence of EOP at five days was 17% in the prophylaxis group and 31% in controls (absolute difference of 14%).³ When using their definition of EOP, the incidence at seven days was 19% in the prophylaxis group and 34% in controls (absolute difference of 15%).

In the TTM trial, pneumonia occurred in 52% of patients treated at 33°C and 46% in those treated at 36°C.⁶⁵ Pneumonia was not defined as early- or late-onset. In a post-hoc analysis, the incidence of pneumonia in patients admitted to centers administering antibiotic prophylaxis was 41% compared to 54% at centers that did not.⁶⁶ Clustering within centers was possible.

Using data from INTCAR, the incidence of pneumonia, which was not defined as early- or late-onset, was 33% with antibiotic prophylaxis. Accordingly, 60 patients will be randomized to each group (n=120 total). This provides 80% power at a two-tailed 5% level of significance to detect an absolute reduction in the incidence of EOP by 25%, from 55% to 30%.

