9.5. Resistome Assessment

Abundance of antibiotic resistance-associated genotypes in resistomes will be compared within and between treatment groups. If ceftriaxone or placebo alters resistomes, ANOVA will be performed across genotypes. The abundance of each genotype will be compared between ceftriaxone- and placebo-treated patients post-intervention by both Student's T test and $\chi 2$ to establish direct changes associated with ceftriaxone and whether those deviate from potential changes in resistomes due to ICU admission. All statistical analyses will be performed using GraphPad Prism 8 (GraphPad Software Inc). A p value <0.05 will be considered significant. To measure the acquisition of ARGs, the increase in number of ARGs relative to baseline samples were compared within each treatment group using the Wilcoxon Signed-Ranks test. In addition, the baseline number and changes in the number of ARGs targeting a prioridefined frequently administered (macrolides, beta-lactams, fluoroquinolones, sulfamethoxazole-trimethoprim, and vancomycin) and infrequently administered (tetracyclines, erythromycin, aminoglycosides, chloramphenicol, clindamycin, fosfomycin, quinupristin) antibiotics according to clinical practice guidelines were compared between treatment groups.^{67,68}

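### The plan states a no-harm hypothesis for the resistome but contains no analysis that could support it

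*Combined protocol and SAP*

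**What the plan says.** Section 2.7 sets out two expectations. Ceftriaxone will reduce early-onset pneumonia (EOP) and T-cell inflammation, and "prophylactic ceftriaxone will not negatively affect bacterial resistomes as assessed by resistance genotypes in stool or sputum". The second is a claim that harm is absent. Section 3 describes the study as a "randomized-controlled, quadruple-blind, non-commercial superiority trial conducted at xxxx".

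Section 9.5 gives the resistome analysis:

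- "Abundance of antibiotic resistance-associated genotypes in resistomes will be compared within and between treatment groups".
- A conditional step follows: "If ceftriaxone or placebo alters resistomes, ANOVA will be performed across genotypes". What would count as an alteration is not defined.
- "The abundance of each genotype will be compared between ceftriaxone- and placebo-treated patients post-intervention by both Student's T test", with a chi-square test alongside it.
- For acquisition of antibiotic resistance genes (ARGs), "the increase in number of ARGs relative to baseline samples were compared within each treatment group using the Wilcoxon Signed-Ranks test".
- Baseline number and change in number of ARGs, grouped by frequently and infrequently used antibiotics, are compared between arms. No test is named.
- The decision criterion is "A p value <0.05 will be considered significant".

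Section 9.5 mentions no confidence interval, acceptable increase or sample-size argument. The 95% interval in section 9.2 belongs to the EOP risk ratio, and section 9.3 carries that approach over to late-onset pneumonia and other infections. The sample size in section 9.1 rests on EOP alone. Section 4.1 accepts missing specimens without recording a deviation.

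**The concern.** A test of difference can give evidence that resistance increased. It cannot by itself give evidence that resistance did not increase. For that, one needs an interval for the between-arm effect, and a statement of which increases it excludes. Without one, the hypothesis in section 2.7 has nothing in section 9.5 that answers it.

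The resistome is not a side issue here. It is in the trial's title. Section 2.2 says the benefits of prophylaxis have to be weighed against the risk of altering resistomes. Section 8.3 gives a complete resistome assessment as one reason not to stop for efficacy, and section 11 puts the resistome data in the main publication. If non-significance came to be taken as support for section 2.7, that support would be easiest to obtain when fewest specimens are available.

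**Working it through.** **1. The plan's own figure.** The only sample size in the documents is for EOP: 55% v 30%, two-sided 5%, 80% power, 60 per arm. The pooled-variance formula, with mean proportion 0.425, is

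n = [1.96·√(2·0.425·0.575) + 0.842·√(0.55·0.45 + 0.30·0.70)]² / 0.25² = 60.2, so 61 per arm. Power at 60 per arm is 79.9%.

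The stated 60 per arm reproduces. It says nothing about the resistome, for which no figure is given.

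**2. Can any analysis in section 9.5 support no harm?**

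- *Per-genotype t and chi-square tests after treatment:* between-arm, but judged only by p<0.05, one genotype at a time.
- *ANOVA across genotypes:* run only if an alteration has been found.
- *Signed-rank test on ARG acquisition:* within each arm. Significance in one arm and not the other is not a comparison of arms.
- *ARGs by antibiotic group:* a between-arm comparison of change, but with no interval or bound.

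None of them can.

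**3. How much could a null result hide?** The documents give no SD, ARG count or relevant difference, so the following are assumptions: a single overall measure, one two-sample t-test, two-sided 5%, true harm d of 0.2 to 0.5 SD, and 60 or 30 evaluable patients per arm. Sixty is the planned maximum. Thirty is half of it, because missing specimens are allowed and section 8.1 expects 40–50% in-hospital mortality. That mortality covers the whole stay, so the share lost before a given swab is unknown.

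With df = 2n − 2 and noncentrality δ = d·√(n/2), the chance of p>0.05 is P(−t* < T < t*), where T is noncentral t. Here t* is 1.980 at n = 60 and 2.002 at n = 30.

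| True harm | δ, n = 60 | p>0.05, 60 per arm | δ, n = 30 | p>0.05, 30 per arm |
|---|---|---|---|---|
| 0.2 SD | 1.10 | 81% | 0.77 | 88% |
| 0.3 SD | 1.64 | 63% | 1.16 | 79% |
| 0.4 SD | 2.19 | 42% | 1.55 | 67% |
| 0.5 SD | 2.74 | 22% | 1.94 | 52% |

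The 95% interval half-width is t*·√(2/n): 1.980 × 0.1826 = 0.36 SD at 60 per arm, and 2.002 × 0.2582 = 0.52 SD at 30 per arm.

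**4. What bound could the trial support?** For a true difference of zero, one-sided 2.5% and 80% power, n per arm = 2·(1.96 + 0.842)²/m² = 15.7/m², for a margin of m SD. This gives 393 per arm for 0.2 SD, 175 for 0.3 SD, 99 for 0.4 SD and 63 for 0.5 SD. Solving the other way, 60 per arm supports m = √(15.7/60) = 0.51 SD, and 30 per arm supports 0.72 SD.

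**The case against.** **No rule on p>0.05 is written.** A reader might infer that the plan commits the trial to reporting a non-significant result as safety. It does not. Section 9.5 says what counts as significant and is silent on the rest. Section 2.5 is descriptive in tone: effects are unknown and will be quantified, and earlier conclusions of no induced resistance are faulted for resting on limited analyses. This stands. What can be said is that non-rejection is the only route the plan leaves to its own hypothesis.

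**The illustration is not the planned analysis.** Section 9.5 runs many unadjusted tests by genotype. If they were independent with no true effect, 10 tests would give at least one p<0.05 with probability 1 − 0.95¹⁰ = 40%, and 20 tests 64%. A reader might take the percentages in the table as the chance that the trial as planned reports no difference. They are not. This stands too, but false positives in either direction do not supply a criterion for no harm.

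**Large harm would be seen.** At 60 per arm, 0.5 SD is detected about 78% of the time. True with full sampling. At 30 per arm it is missed about half the time.

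**Missing swabs are partly handled.** Section 4.1 brings the third rectal swab forward on death, comfort care or discharge. That provision is stated only for the third swab.

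**The aim is subsidiary and a margin would be arbitrary.** The resistome is absent from the outcome lists in section 3.11, and the documents offer no basis for a largest acceptable ARG increase. Both are fair. They argue for estimation rather than a formal margin, but do not rescue the no-harm wording: section 2.7 states it as a study hypothesis and section 9.5 does not call it exploratory.

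**Conclusion.** The concern holds as a mismatch between hypothesis and analysis: a claim of no harm, and only tests of difference to address it. It does not extend to saying that the sponsor will declare safety from a non-significant p-value, because the documents do not say so.

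On the assumptions above, a single overall comparison would exclude only harms larger than about 0.36 SD above the point estimate at 60 per arm, or 0.52 SD at 30 per arm. It would miss a true 0.3 SD harm in roughly three of five trials at full size and four of five at half size. These figures depend strongly on the assumed effect, as the table shows. The mismatch itself depends on none of them.

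The EOP analysis is unaffected. The point is worth acting on because resistance is the risk that the protocol itself sets against the benefit.

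**What to change.** In section 9.5:

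- Name one overall resistome measure, specimen and time point. One option is the between-arm ratio of post-dose ARG count in the rectal swab taken 72–96 hours after the first dose, adjusted for baseline count.
- Report the between-arm estimate with its 95% confidence interval, and the number of evaluable samples per arm.
- State that p>0.05 will not be interpreted as no effect, and that the conclusion will be worded by which increases the upper confidence limit does and does not exclude.

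In section 2.7, recast the aim as estimating the effect of ceftriaxone on the resistome. If the no-harm claim is kept, state and justify an acceptable bound before the resistome data are unblinded. Parts of sections 4.2 and 9.5 are already in the past tense. If that point has passed, only the estimation wording remains open.

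The cost is wording and one extra model, with no new patients or specimens. The downside is that the likely conclusion becomes inconclusive rather than no negative effect.
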